Procedure	During Treatment Cycle 1 Day 1 (1 Cycle = 4 Weeks)	During Treatment Cycle 1 Days 8, 15, and 22 (± 3 Days)	During Treatment Cycle 2 Day 1 (± 3 Days)	During Treatment Cycle 2 Days 8, 15, and 22 (± 3 days)	During Treatment Cycle 3 and beyond Day 1 (± 3 Days)	During Treatment Cycle 3 and beyond Day 15 ^a (± 3 Days)	Notes
							performed only if clinically indicated.
Bone Marrow Biopsy					X		Bone marrow biopsy may be needed to assess bone marrow status if an adequate bone marrow aspirate cannot be attained.
Cytogenetic Testing					X		Bone marrow aspirate sample tube for cytogenetic testing/chromosome analysis to be obtained for evaluation by central laboratory to obtain karyotype. During the study, repeat of bone marrow cytogenetic testing is to be completed whenever a bone marrow aspirate is obtained.
Peripheral Blood Smear					X		Whenever bone marrow aspirate (or biopsy) slides are sent to the central reviewer, a peripheral blood smear slide should also be submitted.
IWG Response Assessment					X		International Working Group (IWG) response assessment will be done at Cycles 3, 6, 9, 12, 15, 18, 21, 24, 30, and 36. After Cycle 36, response assessment for disease relapse will be

Table 2-2: On-treatment Procedural Outline (CA055005)

Procedure	During Treatment Cycle 1 Day1 (1 Cycle = 4 Weeks)	During Treatment Cycle 1 Days 8, 15, and 22 (± 3 Days)	During Treatment Cycle 2 Day 1 (± 3 Days)	During Treatment Cycle 2 Days 8, 15, and 22 (± 3 days)	During Treatment Cycle 3 and beyond Day 1 (± 3 Days)	During Treatment Cycle 3 and beyond Day 15 ^a (± 3 Days)	Notes
							performed only if clinically indicated. Participants should be assessed for CR/CRi status maintenance, relapse after CR/CRi, or disease relapse.
Health Outcomes Assessments							
FACIT-Fatigue Scale and EQ-5D-5L	X		X		X		Each assessment should be completed at the start of the clinic visit prior to dosing and other study assessments. See Section 9.1.2 .
Study Intervention							
Dispense/Administer	X		X		X		IP is scheduled to be taken for 1-14 days of each cycle, unless there has been a schedule modification from 14 days to 7 days of IP administration due to toxicity. Participants with ≥5% to ≤15% blasts in the bone marrow or peripheral blood response assessment may receive 200mg of IP for the first 21 days per cycle.
Provide/Collect Medication Diary	X		X		X		

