9.1 Efficacy Assessments

9.1.1 Efficacy Assessment for the Study

International Working Group Response

International Working Group (IWG) response assessment will be assessed at Cycles 3, 6, 9, 12, 15, 18, 21, 24, 30, 36, and the Treatment Discontinuation Visit. After Cycle 36, IWG response assessment will be performed if clinically indicated at the discretion of the Investigator. Participants should be assessed for CR/CRI status maintenance or disease relapse.

Bone Marrow Aspirate, Biopsy, and Peripheral Blood Smear

Bone marrow aspirate (or biopsy if adequate aspirate is not attainable) samples during the Double-blind Treatment Phase should be collected at Screening, on Day 1 (\pm 7 days) of Cycles 3, 6, 9, 12, 15, 18, 21, 24, 30, 36, and the Treatment Discontinuation Visit. After Cycle 36, bone marrow aspirate collection and evaluation will occur if clinically indicated at the discretion of the Investigator.

Additional bone marrow samples should be collected as clinically indicated. A bone marrow biopsy must be collected if adequate aspirate is not attainable. Whenever a bone marrow sample is collected, a peripheral blood smear is to be prepared.

Instructions for submission of bone marrow samples are provided in Study Reference Manual and/or Study Central Laboratory Manual.

Cytogenetics

Bone marrow cytogenetic testing is to be completed whenever a bone marrow aspirate (or biopsy if adequate aspirate is not attainable; note that specific handling of the biopsy is required if it is to be used for cytogenetics testing [refer to the Laboratory Manual for sample collection, handling, and processing instructions]).

Follow-up AML Therapies

All discontinued participants, regardless of reason for discontinuation, should be followed for subsequent AML therapies every month for the first year and every 3 months thereafter until death, loss to follow-up, withdrawal of consent from further follow-up, or study closure. Subsequent AML therapy follow-up can be performed via the telephone.

Survival Follow-up

All discontinued participants, regardless of reason for discontinuation, should be followed for survival every month for the first year and every 3 months thereafter until death, loss to follow-up, withdrawal of consent from further follow-up, or study closure. The survival follow-up can be performed via telephone.

9.1.2 *Health-related Quality of Life*

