10 STATISTICAL CONSIDERATIONS

10.1 Statistical Hypotheses

The primary endpoint is RFS. Based on the median RFS in the CC-486 and placebo groups of Study CC-486-AML-001, the expected median RFS was set at 4.8 months for placebo, and the expected median RFS was set at 9.5 months for CC-486.

As the primary efficacy analysis, a Cox proportional hazards model will be used to estimate the corresponding hazard ratio and 95% CI for CC-486 relative to placebo. RFS curves will be estimated using Kaplan-Meier (KM) methods. The primary objective of this study is to estimate the efficacy of CC-486 as maintenance therapy by using RFS. The study does not plan to conduct any formal statistical hypothetical testing. For participants who do not have an RFS event, their RFS time will be censored at the last contact date (or "last known RFS date"). RFS will be censored at the date of randomization for participants who were randomized but had no response assessment.

Analysis of the primary endpoint will be conducted when the last subject completes 12 months follow-up. However, it may need to be reconsidered depending on the occurrence status of the event.

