10.4.2 Primary Endpoint(s)

The primary efficacy endpoint of RFS is defined as the time from randomization to the date of documented relapse after CR or CRi per central review, or death from any cause, whichever occurs first. Participants who are still alive without documented relapse after CR or CRi, or who were lost to follow-up without documented relapse, will be censored at the date of their last response assessment. Relapse after CR or CRi is defined according the IWG AML response criteria.

The primary efficacy analysis will be conducted for the ITT Population and will compare the RFS distributions between the two treatment groups. A Cox proportional hazards model will be used to estimate the corresponding hazard ratio and 95% CI for CC-486 relative to placebo. The RFS curves will be estimated for the primary efficacy endpoint, time to the date of documented relapse after CR or CRi or death from any cause, whichever occurs first, using Kaplan-Meier (KM) methods. Kaplan-Meier estimates for median RFS as well as the 25th and 75th percentiles and associated two-sided 95% CIs will be summarized for each treatment group. Plots of the KM survival curves will be presented for the two treatment groups.

Additionally, KM methods will be used to estimate the 1-year and 2-year RFS probabilities for time to death from any cause. Estimates of the 1-year (365 days) and 2-year (730 days) survival probabilities and corresponding 95% confidence intervals will be presented by treatment group.

Additional sensitivity analyses, based on the mITT Population and the ITT Population, will be performed using modified RFS definitions. For these analyses of RFS, participants lost to follow-up without documented relapse will be 1) considered as having an event and 2) considered as having an event if they were randomized to the CC-486 treatment group and censored if they were randomized to the placebo treatment group. The event/censoring time will be the date of the last response assessment.

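### The planned primary cut does not secure the 2-year RFS rate under either stated censoring rule, and trims the 1-year rate under one of them

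*Combined protocol and SAP*

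**What the plan says.** Section 10.1 fixes the cut: "Analysis of the primary endpoint will be conducted when the last subject completes 12 months follow-up". The next sentence leaves it open: "However, it may need to be reconsidered depending on the occurrence status of the event".

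Section 10.4.2 promises landmark rates: "Estimates of the 1-year (365 days) and 2-year (730 days) survival probabilities and corresponding 95% confidence intervals will be presented by treatment group". The sentence before it mixes two endpoints: "KM methods will be used to estimate the 1-year and 2-year RFS probabilities for time to death from any cause".

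The two sections censor RFS differently. In 10.4.2, participants alive without documented relapse, or lost to follow-up without one, "will be censored at the date of their last response assessment". In 10.1, for participants without an RFS event, "their RFS time will be censored at the last contact date", with a last known RFS date given as an alternative.

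The assessment grid is the same in Table 2-2 ("response assessment will be done at Cycles 3, 6, 9, 12, 15, 18, 21, 24, 30, and 36") and in section 9.1.1, which adds the Treatment Discontinuation Visit.

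The protocol summary gives a study duration of 3 years. No accrual period or dropout rate is stated. Section 10.4 warns that some estimates may not be meaningful because of the limited sample size and offers descriptive summaries instead. Section 10.5 plans no interim analysis.

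**The concern.** A landmark rate needs participants observed past the landmark. The cut guarantees the last subject 12 months of calendar follow-up. It does not guarantee a response assessment at or after day 365, and it guarantees nobody 730 days. The two landmarks fall in gaps of the grid: 365 days lies between Cycles 12 and 15, and 730 days between Cycles 24 and 30.

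This matters because the study is a bridge to CC-486-AML-001. Section 3.2 quotes that trial's RFS rates at 1 year (44.9% vs 27.4%) and 2 years (26.6% vs 17.4%), so the landmark rates here will be set beside them. A 2-year value that is missing, or that is zero because the last person under observation relapsed, could be misread in that comparison.

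**Working it through.** **Inputs.** From the protocol: 10 vs 5 participants (10.2); median RFS 9.5 and 4.8 months (10.1); 28-day cycles; the assessment grid above; a cut 12 months after the last entry. Assumed: uniform accrual over A = 6, 12, 18 or 24 months, exponential RFS, no dropout, no cycle delays, and relapses timed exactly rather than at the visit that detects them. With a 3-year study and a 12-month tail, accrual is at most about 36 − 12 = 24 months. A month is 30.4375 days.

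**1. The plan's own figure.** Section 10.2 gives 87% for the probability that the estimated hazard ratio is below 1. Take P = Φ(|ln HR| / √(1/e₁ + 1/e₀)), with HR = 4.8/9.5 = 0.505 and e₁, e₀ the expected events per arm. At A = 12, e₁ = 7.22 and e₀ = 4.58, so P = Φ(0.683/0.597) = 87.4%. For A = 6, 18 and 24 it is 86.7%, 87.8% and 88.1%. The 87% is reproduced, so the event model and the 12-month cut are consistent with it. It does not identify the accrual period.

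**2. Visit days.** Cycle k Day 1 falls 28(k − 1) days after Cycle 1 Day 1: C12 = 308, C15 = 392, C24 = 644, C30 = 812 (each ±7). Randomization may precede Cycle 1 Day 1 by up to 3 days, which changes nothing material.

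**3. One year.** Under last-assessment censoring, an on-treatment participant in remission is known event-free at day 365 only with at least 392 days of follow-up. This affects those randomized within 392 − 365 = 27 days of the last subject. Under last-contact censoring, all 15 can reach day 365.

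With everyone assessed past the landmark, the expected number at risk is 10 × 2^(−11.99/9.5) = 4.2 on CC-486 and 5 × 2^(−11.99/4.8) = 0.9 on placebo. Simulation (20,000 trials per row), last-assessment rule:

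| Accrual (months) | Follow-up too short for day 365 (of 15) | At risk at 1 year, CC-486 / placebo | KM defined, CC-486 / placebo |
|---|---|---|---|
| 6 | 3.2 | 3.3 / 0.70 | 100% / 93% |
| 12 | 2.1 | 3.6 / 0.77 | 100% / 96% |
| 18 | 1.7 | 3.7 / 0.79 | 100% / 96% |
| 24 | 1.6 | 3.75 / 0.79 | 100% / 97% |

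Only those in the second column who are still event-free are actually censored early. The cost is roughly 10 to 21% of the CC-486 number at risk (3.75 or 3.3 against 4.2).

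**4. Two years.** Under last-assessment censoring, a participant needs at least 812 days, so must enter 812 − 365 = 447 days (14.7 months) before the last subject. Under last-contact censoring the gap is 730 − 365 = 365 days (12 months). With nobody at risk at day 730, the Kaplan-Meier value is either undefined (last observation censored) or exactly zero (last observation an event). That share is therefore one minus the probability of at least one participant at risk.

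| Accrual (months) | Rule | At risk at 2 years, CC-486 / placebo | CC-486 undefined | CC-486 undefined or zero |
|---|---|---|---|---|
| 6 | assessment | 0 / 0 | 79% | 100% |
| 6 | contact | 0 / 0 | 90% | 100% |
| 12 | assessment | 0 / 0 | 71% | 100% |
| 12 | contact | 0 / 0 | 79% | 100% |
| 18 | assessment | 0.23 / 0.02 | 48% | 79% |
| 18 | contact | 0.47 / 0.04 | 38% | 62% |
| 24 | assessment | 0.57 / 0.05 | 27% | 56% |
| 24 | contact | 0.77 / 0.07 | 22% | 45% |

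Placebo is undefined or zero in 93 to 100% of trials throughout.

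**5. What more follow-up could give.** With every participant followed past 2 years, the expected number at risk on CC-486 is 10 × 2^(−23.98/9.5) = 1.7. It would be 10 × 0.266 = 2.7 if the CC-486-AML-001 rate applied.

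**The case against.** The strongest reply is that the plan already allows for this. Section 10.1 makes the cut provisional, section 10.4 warns of estimates that are not meaningful, and with 15 participants precision is the binding limit whatever the cut. The hazard ratio and medians remain the main bridging comparators, and no test depends on the landmarks. Part of this stands: even full follow-up leaves about 1.7 CC-486 participants at risk at 2 years. But the provisional sentence is tied to event occurrence, which secures no landmark. The section 10.4 caveat names sample size, whereas with accrual of 12 months or less the cause is the cut itself.

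Slow enrolment, which the risk table in section 3.3.1 anticipates, also helps the plan. At 24 months of accrual the CC-486 2-year value is usually defined. It is still undefined or zero in 45 to 56% of trials.

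A reader might infer more than the documents support:

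- **That the 1-year rate cannot be estimated.** It can. Kaplan-Meier does not need everyone to reach the landmark, a participant censored at day 308 still contributes 308 days, and under the last-contact rule the loss disappears.
- **That the 2-year rate can never be obtained.** Early participants may have more than 24 months at the cut if accrual is slow.
- **That no later analysis will be done.** The protocol describes none for RFS, but it times only the primary-endpoint analysis and section 7.3 refers to a primary database lock. Silence does not show that none is intended.
- **That waiting for everyone to reach Cycle 30 is cheap.** Last entry plus 819 days fits a 3-year study only if accrual takes at most 1095 − 819 = 276 days, about 9 months. Section 5.1 also allows follow-up to end when commercial product becomes available at the site.

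If the landmark rates are meant as overall survival, which the wording in 10.4.2 leaves possible, the response grid does not govern them. With accrual of 12 months or less, the cut still leaves nobody observed alive to day 730.

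**Conclusion.** The point holds in two parts of unequal weight. The 2-year RFS rate by arm is not secured at the planned cut under either censoring rule. No one is at risk with accrual of 12 months or less, and 0.2 to 0.8 CC-486 participants are expected at risk with 18 to 24 months, giving an undefined or zero CC-486 estimate in about 45 to 100% of trials. The 1-year rate is a minor matter. It stays estimable, but under the 10.4.2 rule the numbers at risk fall from 4.2 to between 3.3 and 3.75 on CC-486.

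The conflict between 10.1 and 10.4.2 on the censoring date is a plain contradiction that needs no simulation, and it decides whether the 1-year loss exists at all. The visit arithmetic is exact apart from windows and cycle delays. The percentages rest on the assumed accrual, exponential RFS and absence of dropout.

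**What to change.** 1. Use one RFS censoring rule in 10.1 and 10.4.2. The last response assessment is the better choice, because section 9.1.1 allows survival contacts by telephone and such a contact does not establish remission. State in 10.4.2 that the landmark rates are RFS, not time to death. This is a wording change.

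2. In 10.1, trigger the primary analysis when the last subject has reached the Cycle 15 Day 1 response assessment (392 + 7 days, about day 400), or has had an event or discontinued, and not before the 12 months now specified. The delay is 400 − 365 = 35 days, about five weeks. It restores the expected CC-486 number at risk at 1 year to about 4.2 and needs no new visits.

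3. Do not present the 2-year RFS rate as a primary-cut result. Report it at an end-of-study analysis named in the plan, from whatever follow-up has accrued, with numbers at risk by arm. Do not extend the study to bring every participant to Cycle 30. The cost is later reporting, and precision at 2 years stays poor in any case.

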10.2 Sample Size Determination

The sample size is primarily calculated as approximately 15 based on the feasibility of enrollment taking into consideration of the anticipated difficulty to find candidates who have achieved CR/CRI with conventional intensive chemotherapy in Japan. However, as many participants as possible will be enrolled.

With a sample size of 15 participants, assuming 2:1 ratio to adequately secure the number of participants in CC-486 group and to keep the number in the placebo group to a minimum, then approximately 10 participants will receive CC-486, and approximately 5 participants will receive

placebo. Based on this sample size, the probability that the point estimate of hazard ratio of CC-486 versus placebo becomes less than 1 is 87%).

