- Candidate for allogeneic bone marrow or stem cell transplant at screening.
- Have achieved CR/CRI following therapy with hypomethylating agents
- Received therapy with hypomethylating agents for MDS and went on to develop AML within four months of discontinuing the therapy with hypomethylating agents.

Intervention Groups and Duration:

Total duration of study participation for each participant: screening phase for 4 weeks, treatment phase until AML relapse, and follow-up phase until death, withdrawal of consent, study termination, or loss to follow-up.

Dose regimen: 200 mg once daily of CC-486 or placebo will be taken for the first 14 days of each 28-day treatment cycle.

Dose modification for toxicity and dose/schedule adjustment with AML relapse are allowed.

Study Intervention:

Study Intervention for CA055005		
Medication	Potency	IP/Non-IP/AxMP
CC-486	150mg/200mg	IP
Placebo	150mg/200mg	IP

Abbreviations: AxMP, auxiliary medicinal product; IP, Investigational Product.

Statistical Methods:

The primary efficacy analysis will be conducted for the Intent-to-Treat Population and will compare the RFS distributions between the two treatment groups. A Cox proportional hazards model will be used to estimate the corresponding hazard ratio and 95% CI for CC-486 relative to placebo. The RFS curves will be estimated using Kaplan-Meier methods.

Data Monitoring Committee: No

A Data Monitoring Committee or other review committee will not be used in the study.

Other Committee: No

Other review committee will not be used in the study.

Brief Summary:

CA055-005 is designed as a 2:1 randomization of CC-486 or placebo to assess the efficacy and safety of maintenance treatment with oral azacitidine in a cohort of Japanese participants ≥ 55 years with AML, and in CR/CRi after intensive induction chemotherapy with or without consolidation chemotherapy. The primary endpoint of RFS and the secondary endpoints of OS, safety, PK, and HRQoL will be evaluated and allow for a comprehensive investigation of efficacy, exposure/safety, and appropriateness of the clinical recommended dose for the Japanese population in comparison with the data from Study CC-486-AML-001.

Study Duration: 3 years

Study Intervention Duration: Until AML relapse in each participant.

Study Visit Frequency: On Days 1, 8, 15 and 22 in Cycles 1 and 2, Days 1 and 15 in Cycles 3 through 24, and Day 1 in Cycle 25 and beyond.

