The QUAZAR Study (CC-486-AML-001) has demonstrated that CC-486 maintenance therapy was associated with significantly longer overall and relapse-free survival than placebo among older patients with AML who were in remission after chemotherapy. CC-486 was approved in the

US and Canada in September 2020 and January 2021, respectively, and is indicated for continued treatment of adult patients with AML who achieved first CR/CRI following intensive induction chemotherapy and are not able to complete intensive curative therapy²⁸. An oral formulation of azacitidine (CC-486) has been developed and is currently being evaluated in clinical trials, either as a single agent or in combination with other drugs, for the treatment of hematological and solid malignancies. This oral formulation of azacitidine provides an opportunity for administration in a more convenient outpatient setting rather than in the hospital/clinic setting. Home administration also alleviates the morbidity of injection and catheter-site reactions and avoids the inconvenience and resource utilization costs associated with frequent hospital/clinic visits.

Results from the ongoing Phase 3, randomized, double-blind, placebo-controlled QUAZAR Study (CC-486-AML-001), which enrolled de novo AML and secondary AML participants, have shown that CC-486 (300 mg/day for 14 days of 28-day treatment cycles) as first-line maintenance therapy demonstrated significant and clinically meaningful improvement in OS and relapse-free survival (RFS) in AML in remission following induction chemotherapy with or without consolidation. Median follow-up was 41.2 months. Median OS was 24.7 months with CC-486 versus 14.8 months with placebo (P=0.0009; HR 0.69 [95% CI 0.55, 0.86]). Median RFS was 10.2 months in the CC-486 arm compared to placebo at 4.8 months (P=0.0001; HR 0.65 [95% CI 0.52, 0.81])²⁹. The RFS rate at the 6-month time point was 67.4% in the CC-486 group and 45.2% in the placebo group, for a difference of 22.2%. The RFS rates were consistently higher for the CC-486 group than for the placebo group at each of the later time points (44.9% versus 27.4% at the 1-year time point and 26.6% versus 17.4% at the 2-year time point, respectively).

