5.4 Scientific Rationale for Study Design

This is a multicenter, randomized, double-blind, placebo-controlled, Phase 2 study in Japanese participants ≥ 55 years with AML in CR/CRi following intensive induction therapy with or without consolidation therapy. Participants will be randomized 2:1 to receive 200 mg CC-486 (QD or placebo for the first 14 days of each 28-day treatment cycle. This is a bridging study to provide clinical data that will allow extrapolation of the CC-486-AML-001 study data to Japan.

One of the most important goals of maintenance therapy for AML should be to minimize the risk of relapse and sustain complete remission as long as possible. Study CC-486-AML-001 has shown survival benefit on not only OS but RFS when compared with BSC, and the subgroup analyses of the primary endpoint (OS) and key secondary endpoints (RFS) showed a consistent efficacy benefit of CC-486 across various demographic and disease-related subgroups. Thus, in Study CA055-005, RFS is set as a primary endpoint and OS as a secondary endpoint.

When designing CA055-005 as a randomized, placebo-controlled study, the data of median RFS from both arms of Study CC-486-AML-001 (ie, 10.2 months vs 4.8 months for the CC-486 arm and BSC arm, respectively) were primarily referred to for the statistical sample size calculation.

The target population of this study should be same as that of Study CC-486-AML-to secure comparability between the 2 studies for the purpose of bridging. As for the target age, although most enrolled participants will be elderly (eg, ≥ 60 years or ≥ 65 years), the same target age is set as in Study CC-486-AML-001 (ie, ≥ 55 years) because the survival benefit in Study CC-486-AML-001 was observed regardless of age group.

The 2:1 randomization to CC-486 or placebo will be performed to adequately secure the number of participants in the CC-486 group and to keep the number of participants in the placebo group to a minimum. Best supportive care will include but not be limited to red blood cell (RBC) and platelet transfusions; use of an erythropoiesis-stimulating agent (ESA); antibiotic, antiviral, and antifungal therapy; nutritional support; and granulocyte-colony stimulating factors (G-CSFs) for participants experiencing neutropenic infections. Thus the risk of not providing participants with appropriate care is minimized while providing the potential benefit of maintaining CR/CRi status.

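### Does the 87% chance of a hazard ratio estimate below 1, given in section 10.2 without its assumptions, need restating?

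*Combined protocol and SAP*

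**What the plan says.** Protocol section 10.2 sets the sample size at about 15 on grounds of enrollment feasibility, split about 10 to CC-486 and 5 to placebo. It then gives one operating characteristic: "the probability that the point estimate of hazard ratio of CC-486 versus placebo becomes less than 1 is 87" per cent. No hazard ratio, medians, number of events, accrual period or method is stated there.

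The section just before it, 10.1, gives planning values attributed to AML-001: "the expected median RFS was set at 4.8 months for placebo, and the expected median RFS was set at 9.5 months for CC-486". It says that no formal test is planned, and it fixes the timing: "Analysis of the primary endpoint will be conducted when the last subject completes 12 months follow-up", subject to reconsideration depending on how events occur. Section 5.4 says that the AML-001 medians of 10.2 and 4.8 months "were primarily referred to for the statistical sample size calculation".

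Section 3.2 reports the AML-001 result in two ways. One is medians with a hazard ratio: "Median RFS was 10.2 months in the CC-486 arm compared to placebo at 4.8 months (P=0.0001; HR 0.65 [95% CI 0.52, 0.81". The other is landmark rates: "The RFS rate at the 6-month time point was 67.4% in the CC-486 group and 45.2% in the placebo group", then "44.9% versus 27.4% at the 1-year time point and 26.6% versus 17.4% at the 2-year time point". The protocol summary gives "Study Duration: 3 years".

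**The concern.** A sample size alone cannot determine the probability that a hazard ratio estimate falls below 1. An assumed effect and an event count are needed as well, and section 10.2 states neither. A reader who looks for the effect finds planning medians whose exponential ratio is about 0.505. That is below the lower limit (0.52) of the AML-001 interval for the RFS hazard ratio, and the hazard ratio is what the primary Cox model estimates. The 87% then looks optimistic as well as unexplained.

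The figure has some prominence. It is the only operating characteristic for the primary endpoint of a bridging study that has been cut from 66 to 15 participants. A reader would put the chance of an unfavourable point estimate at 13%. If the true hazard ratio were 0.65, that chance would be closer to one in four, and an estimate above 1 would be weaker evidence against carrying AML-001 over to Japan than the 13% suggests.

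**Working it through.** **Inputs.** 10 and 5 participants, allocation 2/3 : 1/3 (10.2). Planning medians 9.5 and 4.8 months (10.1). AML-001 medians 10.2 and 4.8 months (3.2, 5.4), hazard ratio 0.65, and RFS of 67.4%, 44.9% and 26.6% on CC-486 against 45.2%, 27.4% and 17.4% on placebo at 6, 12 and 24 months (3.2). Analysis 12 months after the last entry (10.1). The accrual period is not stated. A 3-year study leaves at most 36 − 12 = 24 months, so 0, 12 and 24 months are used. No dropout is assumed.

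**Formula.** With D events and 2:1 allocation, the log hazard ratio estimate has variance of about 1/(D × 2/3 × 1/3) = 1/(D × 2/9). Hence P(estimate < 1) = Φ(−ln HR × √(2D/9)).

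**Reproducing the plan's figure from 10.1.** HR = 4.8/9.5 = 0.505 and ln HR = −0.683. With D = 12, √(24/9) = 1.633, and 0.683 × 1.633 = 1.115, so Φ = 0.868. Exactly 87% needs about 12.25 events. Expected events under exponential RFS are 9.95, 11.8 and 12.8 for accrual over 0, 12 and 24 months. Simulation of 10 against 5 participants gives 85.9%, 87.5% and 88.0%.

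**From the medians named in 5.4.** HR = 4.8/10.2 = 0.471 and ln HR = −0.754. With D = 10, √(20/9) = 1.491, and 0.754 × 1.491 = 1.124, so Φ = 0.869. Simulation gives 87.8%, 89.7% and 90.5% (9.7, 11.6 and 12.6 events). So 87% does not identify one pair of medians. The 10.1 pair fits over the whole accrual range, and the 5.4 pair fits when accrual is short.

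**At the AML-001 Cox hazard ratio.** ln 0.65 = −0.431. D = 12 gives 0.431 × 1.633 = 0.703, so Φ = 0.759. D = 15 (every participant has an event) gives 0.431 × 1.826 = 0.786, so Φ = 0.784. Simulation with a 4.8-month placebo median gives 76.0%, 77.7% and 77.9%. Reaching 87% would need about 31 events.

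**Under the AML-001 landmark rates.** Piecewise-exponential curves through the quoted rates, with the last hazard carried forward and the cut-off 12 months after the last actual entry, give 78.8%, 77.4% and 76.6% (9.1, 10.3 and 11.1 events).

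**Why the readings differ.** The ratio of cumulative hazards by interval, from the quoted rates, is:

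- months 0–6: ln 0.674 / ln 0.452 = 0.50
- months 6–12: ln(0.449/0.674) / ln(0.274/0.452) = 0.81
- months 12–24: ln(0.266/0.449) / ln(0.174/0.274) = 1.15

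The effect is concentrated early. The placebo median falls before month 6 and the CC-486 median before month 12, so the ratio of medians mainly reflects the early separation, while a Cox estimate averages over later events too. Exponential curves through 9.5 and 4.8 months give 64.5% and 42.0% at 6 months, a difference of 22.5 points against the quoted 22.2. At 12 months they give 41.7% and 17.7%, a difference of 24.0 points against the quoted 17.5. Most of that gap lies in the placebo arm (17.7% against 27.4%).

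| Assumed effect | P(estimate < 1) | P(estimate ≥ 1) |
|---|---|---|
| Stated in 10.2 | 87% | 13% |
| Medians 9.5 / 4.8 (10.1) | 85.9–88.0% | 12.0–14.1% |
| Medians 10.2 / 4.8 (5.4) | 87.8–90.5% | 9.5–12.2% |
| HR 0.65 (3.2) | 76.0–77.9% | 22.1–24.0% |
| Landmark rates (3.2) | 76.6–78.8% | 21.2–23.4% |

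**The case for a change.** The strongest case for a change is that the primary analysis estimates a Cox hazard ratio, for which AML-001 gives 0.65. Two separate readings of AML-001, that hazard ratio and the landmark rates, agree on 76 to 79%. A planning ratio of about 0.5 is therefore favourable, and a single unqualified figure hides this. Sections 10.1 and 5.4 also differ (9.5 against 10.2 months), so a reader cannot tell which pair was used. Two sentences would settle it.

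Most of this stands as description. It is true that 10.2 omits its inputs, that the median ratios are more favourable than the Cox hazard ratio, and that exponential curves miss the 1-year placebo rate. Three points weigh against acting on it.

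First, AML-001 supports both readings. Its medians and its hazard ratio stand in the same sentence of 3.2, and its own median ratio (0.471) lies further below the interval than 0.505 does. The mismatch comes from the shape of the AML-001 curves and not from a departure from its data in 10.1. If anything, 9.5 months is the more cautious choice beside the observed 10.2.

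Second, the inputs are easy to recover. The medians stand in the section immediately before 10.2, and with no formal test planned they have no other evident use. Reading 9.5 months as a rounded-down planning value and 10.2 as the observed one reconciles the two sections.

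Third, the 76 to 79% range rests on accrual, dropout and curve-shape assumptions that the protocol does not supply, and the analysis date may itself move. It would add a second scenario without correcting the first.

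**Conclusion.** The 87% is sound under the plan's own planning medians: 86.8% by formula at 12 events, and 85.9 to 88.0% by simulation over 0 to 24 months of accrual with no dropout. It also fits the AML-001 medians at about 10 events. At a hazard ratio of 0.65 or under the AML-001 landmark rates it would be about 76 to 79%, some 8 to 11 points lower (87 − 79 = 8, 87 − 76 = 11). That difference reflects which summary of AML-001 is taken as the effect and is not a miscalculation.

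No change to the plan follows. The number of participants is set by feasibility, the study is for estimation only, and no decision rule, analysis or interpretation threshold refers to 87%. The risk table in 3.3.1 already says that so small a study may fail to show results comparable with AML-001, and section 10.4 warns that some estimates may not be meaningful. The unstated inputs are a documentation gap that a statistician can fill from 10.1. Filling it in the text would leave the design, the analysis and every conclusion as they are.
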